10.1.3 Phone call/Virtual Visits (V3-5, V7, V9 and V11)

During the study treatment period, 6 phone call/virtual visits are scheduled between the IMP dispensing visits. The purpose of the contact with the patients is to monitor the patients' compliance with SMPG and insulin titration and to collect injection information, AE/SAE, including hypoglycemia, any change in concomitant medications, and OSES part 1 questionnaire (resource requirement). Resource use questionnaire will be administered on Visits 9 and 11.

Patient of the traditional group will be called by the investigator or qualified designee at a scheduled time. If the call has been completed by site staff other than the investigator, the investigator has to be consulted if AE/SAE is suspected.

Patients of the virtual group will contact the sites and communicate via virtual chat. It can also occur ad-hoc as needed.

During the phone or video, the following will be checked and information collected accordingly:

- Injection of the IMP (Toujeo) and NIMP (the mealtime insulin analogs) as instructed by the investigators
- Occurrence of new medical events, diseases, or symptoms since the last visit
- Occurrence of hypoglycemic events or symptoms, or any injection site reaction
- Change or addition of any new medications since the last visit
- If the patient feels comfortable in handling e-diary, glucose meter and IMP injection device or he/she needs help

Further following procedures will be performed:

- Instruct patients on further insulin dose adjustment according to their SMPG values
- Remind the patients to measure required SMPG and complete the diary
- Remind patients to perform the 7-point SMPG before Visit 10 and Visit 12
- Document change of concomitant medication and actual basal and mealtime insulin doses in the e-CRF
- Report AE/SAE and hypoglycemia if any
- For patients of the traditional group, remind to be fasting prior to Visit 10 and Visit 12; remind and check with the patients of the virtual group to have their blood drawn at the local laboratory (US patients)
- For patients of the traditional group, remind to bring the glucose meter and IMP (used, in-use, or unused) at each onsite visit

For a complete list of procedures scheduled for each phone-call visit please refer to the study flowchart ([Section 1.2](#)).

10.1.4 Onsite/virtual visits (V6, 8, and V10) during treatment period

Three study visits will occur onsite before the EOT for the traditional approach group. Virtual approach group patients will have the corresponding visit as virtual visit.

During these visits, study material (eg, ancillaries and glucose meter accessories) and IMP will be dispensed or shipped, and the patients' progress, SMPG patterns, dose regimens and data collected during the study (eg, hypoglycemia, AE/SAE, average fasting and postprandial SMPGs over the past days) will be discussed. For patients of the traditional group, the IMP dispensation will be done on site by the investigator or pharmacist. For patients of the virtual group, the IMP will be shipped using the DTP service described in [Section 8.1.3](#).

Patients of the traditional group will bring their glucose meter and IMP boxes to the study site at each onsite visit. For patients of the virtual group, the used and unused IMP will be returned to the sites by Marken driver.

Patients of the virtual group will perform all assessments via virtual device for vital signs (BP, HR) and weight measurements.

The investigators and study staff will check and document in the source data if the patient has reached the titration goal or not at each visit. Appropriate titration will be continued until target fasting SMPG without hypoglycemia has been reached.

Investigational medicinal product compliance (collecting and counting used and unused cartridges and syringes) will be checked and addressed with the patients. The IMP compliance will be checked by video chat between the patients of the virtual approach group and the site staff.

Consultation for diet and life-style modification should be provided during the visits if needed.

Overall Study Experience-Sites part 1 questionnaire (resource requirement) should be completed by the Investigator.

Within 1 week prior to Visit 10, patients should be reminded, if needed, to perform at least one day of 7-point SMPG.

Resource use questionnaire will be completed by the patients at Visits 6, 8, and 10.

Additionally, at Visit 10, patients should be fasted and blood will be drawn for measurements of HbA1c and FPG at central laboratory. The patients from the virtual approach group will attend the local Quest laboratory with the study requisition to complete the blood sampling (for patients located in Canada, phlebotomy may be done by the Homecare nurses at the patients' home or other suitable location).

For a complete list of procedures scheduled for each study visit please refer to the study flowchart ([Section 1.2](#)).

10.1.5 End of Treatment (EOT) visit (Visit 12, Week 24)

The EOT visit will occur onsite for the traditional approach group. Virtual approach group patients will have the corresponding visit as virtual visit.

Before the EOT visit, the patients will be reminded to:

- perform at least one day of 7-point SMPG during the week prior to the visit. The visit will be postponed if the patient has not done or missed data point(s) of the 7-point profile
- be fasted for about 8 hours prior to on-site visit (traditional group) or presentation to the local laboratory for blood draw (virtual group)
- bring the glucose meter and used and all unused IMP to the sites (traditional group) or as instructed by the study sites (virtual group)

The following will be performed at the EOT visit:

- Vital signs including BP and HR, body weight will be assessed and collected on site (traditional group) or via virtual device (virtual group)
- The questionnaires at the EOT will be performed electronically by the patients. The following questionnaires will be administered: DTSQs, DTSQc, DDS, HFS, WIWI, WPAI-SP, OSEP part 1 and 2, and RUQ. Investigators will be asked to complete the OSES part 1 and 2 questionnaire. The PROs should be completed prior to any other procedure to ensure no impact of site-patient interaction on responses. A subset of patients will be interviewed ([Section 9.2.3.2](#)).
- Blood sampling for laboratory tests will be done at study site, local Quest laboratory, or by Homecare nurse (virtual group patients in Canada only)
- The last IMP must be injected no earlier than completion of all the EOT assessment. Patients of the traditional group will return all their used and unused IMP to the site for accountability and destruction at the EOT visit. For patients of the virtual group, Marken driver will retrieve all used and unused IMP at patients' home after the EOT visit and will return them to the site for accountability and destruction.
- IRT call will be made to register the EOT for the patient

For a complete list of procedures scheduled for this study visit please refer to the study flowchart ([Section 1.2](#)).

10.1.6 Follow-up Visit (Visit 13)

Following the last administration of IMP either as scheduled or prematurely, a post-treatment follow-up should be scheduled for all the patients in one week (+/- 2 days) after permanent discontinuation of the study treatment. This visit can be a virtual of phone call visit, or an on-site visit in case of ongoing or new AE during the post-treatment period, if needed. The patient is called by the investigator or qualified designee at scheduled time. If the call has not been performed by the investigator, the investigator has to be consulted if AE/SAE and hypoglycemic event are suspected.

During the phone call the same set of questions as listed for other telephone/virtual visits has to be asked ([Section 10.1.3](#)), except IMP-related questions.

10.2 DEFINITION OF SOURCE DATA

10.2.1 Source data to be found in patient's file

For both patient groups, all evaluations recorded in the e-CRF must be supported by appropriately signed source documentation related but not limited to the following:

- Agreement and signature of informed consent form with the study identification; the signed electronic informed consent form will be printed from the study web portal
- Study identification (name)
- Patient number, confirmation of randomization, approach group, treatment batch number, dates and doses of study medication administration
- Medical, surgical, diabetes history, including information on :
 - Demography, inclusion and exclusion criteria
 - Last participation in a clinical trial
 - Contraception method for WOCBP
 - Previous and concomitant medication
- Dates and times of visits and assessments including examination results (vital signs, height, body weight, laboratory reports)
- For patients of the virtual group, the data transferred directly from Bluetooth devices to the study web portal will be considered as source data and will not have to be recorded in the patient file
- Insulin dose (both basal and mealtime) titration assessment and recommendation for insulin dose adjustment
- Investigator/physician notes, nursing notes, dietician's notes
- AEs and AEs follow-up,
 - In case of SAE, the site should file in the source documents at least copies of the hospitalization reports and any relevant examination reports documenting the follow-up of the SAE
- Date of premature study discontinuation (if any) and reason.
- Patient eDiaries

A monitor will visit the sites to verify the accuracy of the source data listed above against patient's files.

10.2.2 Source data verification requirements for screen failures

For screen failure patients, the following source data must be verified: patient's identification details, the informed consent signed by the patient, the study identification (name), dates of study visits, and the main reasons for screen failure.

10.3 HANDLING OF PATIENT TEMPORARY OR PERMANENT TREATMENT DISCONTINUATION AND OF PATIENT STUDY DISCONTINUATION

The IMP should be continued whenever possible. In case the IMP is stopped, it should be determined whether the stop can be made temporarily; permanent IMP discontinuation should be a last resort. Any IMP discontinuation should be fully documented in the e-CRF. In any case, the patient should remain in the study as long as possible.

10.3.1 Temporary treatment discontinuation with investigational medicinal product

Temporary treatment discontinuation may be considered by the investigator because of suspected AEs. Reinitiation of treatment with the IMP will be done under close and appropriate clinical/and or laboratory monitoring once the Investigator will have considered according to his/her best medical judgment that the responsibility of the IMP(s) in the occurrence of the concerned event was unlikely and if the selection criteria for the study are still met (refer to [Section 7.1](#) and [Section 7.2](#)).

Patients will have to document any temporary discontinuation of the IMP insulin in the diary (date/time of last injection of the IMP insulin; date/time of resuming IMP insulin injection). It is in the interest of the patient to monitor plasma glucose during the temporary discontinuation period, therefore SMPG or other regular determination of plasma glucose is to be performed and documented.

For all temporary treatment discontinuations, duration should be recorded by the investigator in the appropriate pages of the e-CRF.

Temporary treatment discontinuation decided by the investigator corresponds to more than 1 dose not administered to the patient.

10.3.2 Permanent treatment discontinuation with investigational medicinal product

Permanent treatment discontinuation is any treatment discontinuation associated with the definitive decision from the Investigator or the patient not to re-expose the patient to the IMP at any time.

10.3.3 List of criteria for permanent treatment discontinuation

The patients may withdraw from treatment with the IMP if they decide to do so, at any time and irrespective of the reason, or this may be the Investigator's decision. All efforts should be made to document the reason(s) for treatment discontinuation and this should be documented in the e-CRF.

Criteria for permanent treatment continuation include:

- At the patient's own request, eg, withdrawal of consent for treatment

- If, in the investigator's opinion, continuation with the administration of the study treatment would be detrimental to the patient's well-being, (eg, requiring treatment with insulin pump)
- Pregnancy
- Specific request of the sponsor.

10.3.4 Handling of patients after permanent treatment discontinuation

Patients will be followed up according to the study procedures specified in this protocol up to the scheduled date of study completion, or up to recovery or stabilization of any AE to be followed-up as specified in this protocol, whichever comes last.

As far as possible, and after the permanent discontinuation of treatment, the patients will have a week-24 visit (on-site for traditional, remote for virtual approach group) with all assessments, except those related to IMP, performed as planned 24 weeks after randomization.

After permanent discontinuation of the IMP, patients will return to standard of care for T1DM management based on investigator and patient healthcare providers' clinical recommendation.

Since the IMP, insulin Toujeo is approved basal insulin available in the market. It can be prescribed by the physician if deemed by the Investigator as the best option to manage the diabetes.

All cases of permanent treatment discontinuation should be recorded by the Investigator in the appropriate pages of the e-CRF when considered as confirmed.

10.3.5 Procedure and consequence for patient withdrawal from study

The patients may withdraw from the study before study completion if they decide to do so, at any time and irrespective of the reason. Withdrawal of consent for treatment should be distinguished from withdrawal of consent for follow-up visits and from withdrawal of consent for non-patient contact follow-up, eg, medical records check. Patients requesting withdrawal should be informed that withdrawal of consent for follow-up may jeopardize the public health value of the study.

If possible, the patients are assessed using the procedure normally planned for the end-of-study visit.

Patients who withdraw should be explicitly asked about the contribution of possible AEs to their decision to withdraw consent, and any AE information elicited should be documented. Preferably the patient should withdraw consent in writing and, if the patient or the patient's representative refuses or is physically unavailable, the site should document and sign the reason for the patient's failure to withdraw consent in writing.

All study withdrawals should be recorded by the investigator in the appropriate screens of the e-CRF and in the patient's medical records when considered as confirmed. In the medical record, at least the date of the withdrawal and the reason should be documented.

For patients who fail to attend the EOT visit, unless the patient withdraws consent for follow-up, the Investigator should make the best effort to recontact the patient (eg, contact patient's family or private physician, review available registries or health care databases), and to determine his/her health status, including at least his/her vital status. Attempts to contact such patients must be documented in the patient's records (eg, times and dates of attempted telephone contact, receipt for sending a registered letter).

The statistical analysis plan will specify how these patients lost to follow-up for their primary endpoints will be considered.

Patients who have withdrawn from the study cannot be rerandomized (treated) in the study. Their inclusion and treatment numbers must not be reused.

10.4 OBLIGATION OF THE INVESTIGATOR REGARDING SAFETY REPORTING

10.4.1 Definitions of adverse events

10.4.1.1 Adverse event

An AE is any untoward medical occurrence in a patient or clinical investigation patient administered a pharmaceutical product and which does not necessarily have to have a causal relationship with this treatment.

10.4.1.2 Serious adverse event

A SAE is any untoward medical occurrence that at any dose:

- Results in death, or
- Is life-threatening, or
Note: The term "life-threatening" in the definition of "serious" refers to an event in which the patient was at risk of death at the time of the event; it does not refer to an event which hypothetically might have caused death if it were more severe.
- Requires inpatient hospitalization or prolongation of existing hospitalization, or
- Results in persistent or significant disability/incapacity, or
- Is a congenital anomaly/birth defect
- Is a medically important event
Medical and scientific judgment should be exercised in deciding whether expedited reporting is appropriate in other situations, such as important medical events that may not be immediately life-threatening or result in death or hospitalization but may jeopardize the patient or may require medical or surgical intervention (ie, specific measures or corrective treatment) to prevent one of the other outcomes listed in the definition above.

Note: The following list of medically important events is intended to serve as a guideline for determining which condition has to be considered a medically important event. The list is not intended to be exhaustive:

- Intensive treatment in an emergency room or at home for:
 - Allergic bronchospasm
 - Blood dyscrasias (ie, agranulocytosis, aplastic anemia, bone marrow aplasia, myelodysplasia, pancytopenia, etc),
 - Convulsions (seizures, epilepsy, epileptic fit, absence, etc).
- Development of drug dependence or drug abuse
- Alanine transaminase (ALT) >3 x upper limit normal (ULN) + total bilirubin >2 x ULN or asymptomatic ALT increase >10 x ULN
- Suicide attempt or any event suggestive of suicidality
- Syncope, loss of consciousness (except if documented as a consequence of blood sampling)
- Bullous cutaneous eruptions

10.4.1.3 Adverse event of special interest

An AESI is an AE (serious or nonserious) of scientific and medical concern specific to the Sponsor's product or program, for which ongoing monitoring and immediate notification by the investigator to the Sponsor is required. Such events may require further investigation in order to characterize and understand them. AEs of special interest may be added, modified or removed during a study by protocol amendment.

- Pregnancy occurring in a female participant entered in the clinical trial.
 - In the event of pregnancy in a female participant, IMP should be discontinued.
 - Follow-up of the pregnancy in a female participant is mandatory until the outcome has been determined (see [Appendix A](#)).
- Symptomatic overdose (serious or nonserious) with IMP/NIMP
 - An overdose (accidental or intentional) with the IMP/NIMP is an event suspected by the Investigator or spontaneously notified by the patient (not based on systematic IMP count) and resulting in clinical symptoms and/or signs and considered a "significant overdose" by the Investigator.
- Reportable by Canadian sites – not applicable to other countries: unusual lack of efficacy for IMP (serious or nonserious)
 - An unusual lack of efficacy is when a health product fails to produce the expected pharmacological or therapeutic benefit and there may be an adverse outcome for the patient, including an exacerbation of the condition for which the medication is being taken. Since no health product can be expected to be effective in 100% of the patients, clinical judgment should be exercised by a qualified health care professional to determine if the problem reported is related to the product itself, rather than one of treatment selection or disease progression. One example of unusual failure in efficacy is a previously well-stabilized condition that deteriorates when the patient changes to a different brand or receives a new prescription.

10.4.2 General guidelines for reporting adverse events

- All AEs, regardless of seriousness or relationship to IMP/NIMP, spanning from the signature of the informed consent form until the end of the study as defined by the protocol for that patient, are to be recorded on the corresponding page(s) or screen(s) of the e-CRF (or the pre-screening log for the patients who will have consented to the study but will not be assigned a patient number, eg, because they are ineligible).
- For patients of the virtual group, any symptom will be entered by the patients in the eDiary. The investigator will be informed through the study web portal and will document the corresponding AEs in the e-CRF.
- Whenever possible, diagnosis or single syndrome should be reported instead of symptoms; if not possible, then each symptom must be reported separately as an AE (eg, nausea, headache). The Investigator should specify the date of onset, intensity, action taken with respect to IMP, corrective treatment/therapy given, additional investigations performed, outcome, and his/her opinion as to whether there is a reasonable possibility that the AE was caused by the IMP or by the study procedure(s).
- The Investigator should take appropriate measures to follow all AEs until clinical recovery is complete and laboratory results have returned to normal, or until progression has been stabilized, or until death, in order to ensure the safety of the patients. This may imply that observations will continue beyond the last planned visit per protocol, and that additional investigations may be requested by the monitoring team up to as noticed by the Sponsor.
- When treatment is prematurely discontinued, the patient's observations will continue until the end of the study as defined by the protocol for that patient.
- Laboratory, vital signs or electrocardiogram abnormalities are to be recorded as AEs only if:
 - Symptomatic and/or
 - Requiring either corrective treatment or consultation, and/or
 - Leading to IMP discontinuation or modification of dosing, and/or
 - Fulfilling a seriousness criterion, and/or
 - Defined as an AESI

Instructions for AE reporting are summarized in [Table 6](#).

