- c* At the end of screening, investigators will determine the eligibility of the screened patients for participation. The randomization IRT call will be made at the Visit 2- Step 1. Patients will be informed by the study sites of their randomization group and Visit 2- Step 2 will be scheduled for the baseline assessments within 1 week (+/- 4 days).
Glucose meters with Bluetooth access and associated accessories (lancet, control solutions, test strips, etc), e-diaries features, and instructions will be shipped to all eligible patients. Patients will use the study provided glucose meters throughout the study.
- d* Physical examination will be performed at the in-person visit in the traditional group. In the virtual group, physical examination will be performed on-site, in-person, between randomization IRT call and the first IMP administration. All other assessments will occur remotely on the day of the first IMP administration (Day 1).
- e* Only for patients randomized in virtual group:
- They will receive the Bluetooth devices for their remote participation and the IMP (Toujeo®) before Visit 2-Step 2.
 - Shortly after randomization (IRT call), they will be scheduled for an in-person visit to allow for the initiation physical examination performed by the investigator.
 - They will be further trained on the Bluetooth devices utilization.
 - The IMP starting date and dose will be instructed by the investigator at the time of Visit 2-Step 2. The first IMP (Day 1) data will be documented with the dose in the e-CRF.
 - All study assessments, including vital signs and weight, will be done via the Bluetooth devices by the patients at home.
 - Patients located in the United States (US) will receive a laboratory requisition and have their blood drawn at any local Quest®. For patients located in Canada, blood draw will be performed by the Homecare via The MRN.
 - Unscheduled on-site visits or Homecare physician visits (depending on the patient's location) only for safety assessment could be scheduled as deemed necessary by the investigator (ie, performance of physical examinations is critical to determine a diagnosis or further evaluation procedure for an AE).
- f* IMP dose will be titrated at the investigator's discretion to achieve the fasting glycemic target while avoiding hypoglycemia

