10 STUDY PROCEDURES

This is an approximately 28-week outpatient study. Screening procedures will be performed as a virtual visit followed by a Homecare in-person visit. Eligible and consenting patients will be randomized to an approach group at telephone Visit 2-Step 1, which will determine the way the next visits are organized:

- Traditional group: 5 onsite visits and 7 telephone visits
- Virtual group: 11 virtual visits and 1 mixed onsite-virtual visit (Visit 2-Step 2)

Additional, optional virtual or telephone visits (according to the approach group) will be scheduled to monitor and support the progress of insulin titration whenever considered necessary by the investigator. For both groups, unscheduled onsite visits or Homecare physician visits (depending on the patient's location) may be scheduled only for safety assessment if deemed necessary by the investigator (ie, performance of physical examinations is critical to determine a diagnosis or further evaluation procedure for an AE).

All onsite visits should take place in the morning at approximately the same time. On the day before each onsite visit, patients should be reminded to bring the medical devices (glucose meter), diaries and IMP (used, in-use or unused) to sites and to be in the fasted status if required at some visits.

The **fasting condition** is defined as an overnight fast no less than 8 hours that consisted of no food or liquid intake, other than water. IMP and noninsulin antidiabetic medication should be administered after the fasting blood sample is drawn for all laboratory tests.

Note: If the patient is not in fasting conditions at visits which required in fasting conditions, the blood sample is not collected and a new appointment should be given to the patient for the following day if possible, with instruction to be fasted.

For phone-call visits and virtual visits, the patient is called by the investigator or qualified designee at a scheduled time.

A visit window of ± 3 days using the day of Visit 2-Step 2 as reference is acceptable (4 days for Visit 6, Visit 8, and Visit 10).

If one visit date is changed, the next visit should take place according to the original schedule, ie, counting from Day 1 on Visit 2-Step 2.

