10.1.2 Randomization Visit (Visit 2)

10.1.2.1 Visit 2-Step 1 (Week -1)

Visit 2-Step 1 telephone call will occur about 1 week after Visit 1-Step 2 when the investigator has received laboratory reports for the screened patients in order to assess exclusion criteria [E 03](#) and [E 12 \(Section 7.2\)](#). The eligible patients will be randomized to the study group through IRT.

Appropriate study materials will be shipped to eligible patients: Bluetooth blood glucose meter with associated accessories (lancets, control solutions, test strips etc.), e-diaries features, and instructions. Bluetooth devices (pulse oximeter, BP cuff, and scale) will be shipped to patients allocated to the virtual group. Bluetooth devices are listed in Appendix E.

Patients of the virtual group will record any symptoms in the eDiary so that the investigator is informed through the study website portal and will record the AE into the e-CRF.

An onsite visit will be scheduled within a week (+/- 4 days) for the traditional group.

Patient randomized in the virtual group will also be scheduled for an onsite visit, but for physical examination only. The virtual Visit 2-Step 2 visit will be scheduled within 1 week (+/- 4 days) of the Visit 2-Step 1 for the virtual group.

Patients should be reminded to perform at least one day of 7-point SMPG prior to the Visit 2-Step 2 visit. Patients of the traditional group will be reminded to bring the glucose meter to the study visit.

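### Only the virtual group enters symptoms in the eDiary, so a difference in non-serious TEAEs compares AE reporting under the two approaches and cannot be read as a difference in true safety

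*Protocol*

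**What the plan says.** The instruction to enter symptoms is given to the virtual group alone. Protocol 10.4.2 states "For patients of the virtual group, any symptom will be entered by the patients in the eDiary", and Protocol 10.1.2.1 puts the start at the randomization call: "Patients of the virtual group will record any symptoms in the eDiary so that the investigator is informed through the study website portal". Protocol 10.1.2.2 repeats the contrast at baseline: AEs since Visit 1 go into the eDiary for the virtual group and are simply documented for the traditional group. I found no instruction telling traditional-group patients to enter general symptoms.

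Both groups are also questioned at scheduled contacts. Protocol 10.1.3 says "Patient of the traditional group will be called by the investigator or qualified designee at a scheduled time" and "Patients of the virtual group will contact the sites and communicate via virtual chat". The items checked are common to both groups and include "Occurrence of new medical events, diseases, or symptoms since the last visit".

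On analysis, safety under the two approaches is a secondary objective (Protocol 5.2, SAP 1.2.2). AE results are shown as numbers and percentages by approach group (Protocol 11.4.3.4 and 11.4.3.4.2, SAP 2.4.5.2), and SAP 2.4.5 describes the safety analysis as essentially descriptive, with no systematic testing. Neither document asks how an AE was first reported. The open-label safeguard in Protocol 8.3 names HbA1c and FPG, not AEs.

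**The concern.** The virtual group has the same scheduled questioning as the traditional group plus a continuous channel that alerts the investigator. Mild, short events are the ones most likely to be entered in a diary and forgotten by the next contact. If more non-serious TEAEs appear in the virtual group, the planned tables cannot say whether more events occurred or more were found.

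Two reporting rules can enlarge the effect. Where no diagnosis is available, each symptom is a separate AE (Protocol 10.4.2). An HLT enters the common-TEAE table once it reaches 2% in either group (SAP 2.4.5.2); 0.02 x 75 = 1.5, so two patients in a group of the planned size are enough.

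At stake is how the safety objective is read, and what a pilot meant to precede full-scale studies (Protocol 4) passes on to them.

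**Working it through.** **1. Contacts per group.** Protocol 10 gives "Traditional group: 5 onsite visits and 7 telephone visits" for one group and 11 virtual visits plus 1 mixed visit for the other. Counting the flow chart (Protocol 1.2) from Visit 2-Step 2 to Visit 13:
- Traditional: 5 on-site (Visits 2-Step 2, 6, 8, 10, 12) + 7 telephone (Visits 3, 4, 5, 7, 9, 11, 13) = 12.
- Virtual: 1 mixed (Visit 2-Step 2) + 11 virtual (Visits 3 to 13) = 12.

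The stated figures reproduce. Scheduled contact frequency does not differ; the eDiary channel does.

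**2. Spacing.** Contacts from the start of treatment to its end fall at Weeks 0, 1, 2, 3, 4, 6, 8, 12, 16, 20 and 24.
- Gaps: 7, 7, 7, 7, 14, 14, 28, 28, 28, 28 days (sum 168 days = 24 weeks).
- Share of treatment in 4-week gaps: 4 x 4 = 16 of 24 weeks, or 67%.
- Longest gap using the visit windows (±3 days; ±4 days for Visits 6, 8 and 10): Week 8 to Week 12 = 28 + 4 + 3 = 35 days.

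**3. Illustrative size.** The documents give neither AE incidence nor capture rates, so every input here is an assumption: true incidence of any AE is 50% in both groups, capture is 90% or 80% in the virtual group, and 70% in the traditional group.

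With one AE per affected patient, observed incidence = 0.50 x capture. With several AEs possible (Poisson events with the same 50% incidence, each detected independently), observed incidence = 1 − 0.5^capture.

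| Capture, virtual vs traditional | One AE per patient | Gap | Poisson events | Gap |
|---|---|---|---|---|
| 90% vs 70% | 45% vs 35% | 10 points | 46.4% vs 38.4% | 8 points |
| 80% vs 70% | 40% vs 35% | 5 points | 42.6% vs 38.4% | about 4 points |

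A wider range, with 100% virtual capture, 50% to 90% traditional capture and 0.5 to 2 true AEs per patient over 24 weeks, gives spurious gaps of about 3 to 24 points.

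**4. Against sampling error.** For 45% versus 35% with 75 per group, the 95% half-width is 1.96 x sqrt(0.45 x 0.55/75 + 0.35 x 0.65/75) = 0.156, about 16 points. SAP section 2 reports 15 randomized. With an assumed 8/7 split and 50% incidence it is 1.96 x sqrt(0.25/8 + 0.25/7) = 0.507, about 51 points.

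**The case against.** The strongest reply is that remote symptom entry belongs to the virtual approach, as video visits and Bluetooth vital signs do. Both groups receive the same IMP, so no drug contrast is at stake, and a difference in AE capture is partly what the trial set out to learn. This stands. A reader might infer that the AE comparison by approach is invalid, but the documents do not support that. It is valid as a comparison of reporting and fails only when read as a comparison of true safety.

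Other replies that stand:
- AE analysis is descriptive. That limits formal claims, although side-by-side percentages are still read as a comparison.
- Serious TEAEs and TEAEs leading to discontinuation already have their own tables (SAP 2.4.5.2).
- The traditional group does not depend on recall alone. Staff review the patient diary at each visit (Protocol 9.2.2.2.2), unscheduled safety visits are possible in both groups (Protocol 10), and on-site staff may notice signs. More AEs in the virtual group is therefore the likely direction, not a certain one.

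Two further readings go too far. From "e-diaries features, and instructions will be shipped to all eligible patients" (flow chart, footnote c) one might conclude that symptom entry could simply have been switched on for everyone; that text does not show that the symptom module and portal alert work in both groups. Nor does the point extend to non-serious hypoglycemia, the one safety endpoint with planned odds and rate ratios: it is diary-captured in both groups and is not reported as an AE (Protocol 9.2.2.2.2 and 9.2.4.4.2).

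**Conclusion.** The asymmetry is in the text and the plan makes no allowance for it. A between-approach difference in non-serious TEAEs shows how much each approach reports; it does not show which approach is safer.

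Its size is unknown. The gaps of 8 to 10 and 4 to 5 points rest wholly on assumed incidence and capture rates and on equal true risk in the two groups. At the planned size the larger gap would lie inside the sampling error for a single comparison. With 15 randomized and only basic descriptive statistics to be produced, the practical effect on this trial's results is small. What remains is a cheap improvement to the report and to any larger trial built on this design.

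**What to change.** 1. **Record the source.** For each AE, state whether it was first reported by eDiary entry or at a contact. In a continuing or future trial this is one e-CRF field. For the 15 randomized patients it is a listing column derived from eDiary dates and times where these are available; SAP 2.4.7 and 2.5.4 handle other e-diary data by date and time of collection, but neither document confirms this for symptom entries.
2. **Show the bounds.** Tabulate virtual-group TEAEs with all events and again without eDiary-first events. The first is an upper bound and the second a lower bound on what contact-only capture would have found, since some eDiary-first events would also have come out at the next contact.
3. **Limit the reading.** Base any between-approach statement about safety on the planned serious-TEAE and discontinuation tables, and say in the report that non-serious TEAE differences reflect reporting as well as occurrence.

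The cost is minor data entry and one table.

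Two alternatives are weaker. Restricting to events elicited or confirmed at a scheduled contact does not equalize capture, because an eDiary entry can prompt the confirmation. Giving the traditional group the same symptom diary would equalize it, but it changes the comparator.
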